10.1 Duration of therapy

We anticipate each individual patient's duration of therapy to be approximately 5 months. In the absence of treatment delays due to adverse event(s), patients will be followed until any one of the following:

- Death
- Unacceptable toxicity
- Symptomatic deterioration
- Investigator's decision to discontinue treatment
- Patient decision to discontinue treatment
- Patient withdraws consent
- Lost to follow up

In the event of a patient's withdrawal, the Investigator will make every effort to complete the End of Treatment procedures specified in the Schedule of Events.

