5.3 Interruption/Disruption of Treatment

Duvelisib is a BID medication. Doses that are missed or not absorbed (i.e., vomiting) will not be made up with additional dosing after the 8 to 15 day study period.

Duvelisib can be stopped for any clinically significant toxicity, including if any of the following are observed:

- Grade 3 or 4 hematologic toxicity (19) as defined by the CTCAE version 5.0)
- Grade 3 or 4 non-hematological toxicity

For grades 1-2 as defined by the CTCAE, will not have any dose modifications and will be treated with supportive care. If study drug is stopped due to an AE, it will not be resumed, and the patient may proceed to leukapheresis on schedule. No allowance will be made for dose interruptions

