10.2 Duration of follow-up

Patients will be followed for approximately 90 days after infusion of tisagenlecleucel product. Patient records may be reviewed until death to assess progression and survival. Survival information may be collected by clinic visit, email, or telephone after ending protocol treatment and until the study is terminated, the patient dies, or the patient is lost to follow-up.

A patient will be considered lost to follow-up if he/she fails to return for three scheduled visits and is unable to be contacted by the study site staff after three attempts at contact by phone.

The following actions must be taken if a patient fails to return to the clinic for a required study visit:
The site will attempt to contact the patient and reschedule the missed visit and counsel the participant on the importance of maintaining the assigned visit schedule and ascertain if the patient wishes to and/or should continue in the study.

Patients removed from study for unacceptable adverse event(s) will be followed until resolution or stabilization of the adverse event.

- Immunogenicity samples will be taken as per schedule of events

Protocol Title: Duvelisib Exposure to Enhance Immune Profiles of T Cells in Patients with Diffuse Large B Cell Lymphoma (DEEP T CELLS)

Patients who have not initiated a new antineoplastic regimen will have the following assessments:

- Radiologic tumor assessments at 90 days
- In case of a clinically significant AE, patient will be followed for safety until resolution or permanent sequelae of all toxicities attributable to study drug(s). If the patient discontinues study drug for a clinically significant AE, the patient will be followed until resolution of the AE or the event is considered to be stable and/or chronic.

11. Inclusion and Exclusion Criteria

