Due to possible increased potency and increased toxicity risk-profile of tisagenlecleucel manufactured from the mononuclear cell apheresis product collected following treatment with duvelisib, all SAE that are collected will be reported to Novartis within 24 hours according to the following Table:

Interventional Clinical Trial WITH Tisagenlecleucel	
Collection by Sponsor	Transfer to Novartis

• All SAEs• All non-serious AEs• All reports of drug exposure during pregnancy and pregnancy outcome. Pregnancy and pregnancy outcome should also be collected for the female partner of any male patient who was treated with tisagenlecleucel, provided consent has been obtained from the female partner.• All reports of abuse and misuse of an investigational medicinal product, other medication errors and uses outside of what is foreseen in the protocol (irrespective if a clinical event has occurred).	
Within 24 hours of awareness, transfer the following safety events:
 
• All collected SAEs in patients exposed to tisagenlecleucel• All collected reports of tisagenlecleucel exposure during pregnancy and pregnancy outcome. All collected reports of pregnancy and pregnancy outcome of the female partner of any male patient who was treated with tisagenlecleucel, provided consent has been obtained from the female partner.• All collected reports of abuse and misuse of tisagenlecleucel.

In particular, any episode of CRS or neurotoxicity grade 2 or greater observed within the first 100 days after tisagenlecleucel infusion will be reported to Novartis.

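### Sections 10.1 and 10.2 let toxicity, deterioration or a decision to stop treatment end follow-up, against the plan's own 90-day rules, which leaves mainly 90-day PFS and OS open to informative loss

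*Combined protocol and SAP*

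**What the plan says.** **Rules that end follow-up early.** Section 10.1 puts therapy at about 5 months and continues: "In the absence of treatment delays due to adverse event(s), patients will be followed until any one of the following". Among the seven events listed are "Unacceptable toxicity", symptomatic deterioration, "Investigator's decision to discontinue treatment" and the matching decision by the patient. Withdrawal of consent and loss to follow-up are separate items, so the toxicity and treatment-decision items end follow-up in their own right.

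Section 10.2 adds: "Patients removed from study for unacceptable adverse event(s) will be followed until resolution or stabilization of the adverse event". A later bullet in 10.2 applies a similar end point (the event resolves, or is stable or chronic) to a patient who discontinues study drug for a clinically significant adverse event.

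**What can happen to these patients next.** Section 5.3: "If study drug is stopped due to an AE, it will not be resumed, and the patient may proceed to leukapheresis on schedule".

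**Rules that point the other way.** Section 10.2 opens with "Patients will be followed for approximately 90 days after infusion of tisagenlecleucel product" and makes no exception for patients who stopped duvelisib. Section 18.4 makes adverse event recording mandatory from enrollment to Day 90 after infusion, including after study treatment has ceased. Section 18.3 gives tisagenlecleucel its own window, from infusion to Day 90. On survival, 10.2 says: "Survival information may be collected by clinic visit, email, or telephone after ending protocol treatment".

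**The concern.** One list serves both as the end of therapy and as the end of follow-up. A site that follows it literally could close a patient's follow-up for toxicity or deterioration while that patient is still on the way to infusion, or is inside the 90 days after it.

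The patients affected are selected by outcome: those with toxicity or who are deteriorating. Section 18.4 explains why post-infusion data in duvelisib-exposed patients matter: "Due to possible increased potency and increased toxicity risk-profile of tisagenlecleucel manufactured from the mononuclear cell apheresis product collected following treatment with duvelisib". The endpoints at stake are secondary: 90-day PFS and OS, and the ICU transfer, tocilizumab or corticosteroid and toxicity summaries (items 6 to 8 of 17.5.3).

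**Working it through.** The plan gives no figure to reproduce here. The check compares the passages, then gives a size illustration on stated assumptions.

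**1. Which treatment does 10.1 mean?** Duvelisib lasts at most 15 days (5.1), product is expected about 4 weeks after collection (7.1), and follow-up is about 90 days after infusion (10.2). 15 + 28 + 90 = 133 days, or 133/30.4 = 4.4 months. Adding the 14-day screening window gives 147 days, or 4.8 months. So the 5 months in 10.1 fits the whole pathway, not the duvelisib course alone. Two readings follow:

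- *Treatment is duvelisib.* A patient who stops it for toxicity, or by decision, leaves follow-up before infusion.
- *Treatment is the whole pathway.* Stopping duvelisib alone does not trigger the treatment-decision items. Unacceptable toxicity and symptomatic deterioration still end follow-up, before or after infusion.

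Either reading can end follow-up before Day 90 and so conflicts with the opening of 10.2.

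**2. Can the 10.2 adverse event rule end before infusion?** Release takes about 3 to 4 weeks from the start of manufacturing (4.1.4). A duvelisib event can resolve or stabilise in that time. Read as the limit of follow-up, the rule would close before CRS could occur.

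**3. What is protected, endpoint by endpoint.**

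| Outcome | Protected by | Left open |
|---|---|---|
| Adverse events, CRS, neurotoxicity | Mandatory recording to Day 90 (18.4); tisagenlecleucel window (18.3); reporting of grade 2 or higher CRS or neurotoxicity to the cell manufacturer for 100 days (18.4); chart review (7.4); any exposure evaluable for toxicity (17.5.1) | Little. Section 18.1 stops recording at withdrawal or trial completion, so it still matters when a patient counts as off study |
| ICU transfer, tocilizumab or corticosteroids | Chart review of ICU transfers (17.4); treatment of an event entered on the adverse event form (18.4) | A smaller gap: not tied by name to the Day 90 rule |
| 90-day PFS and OS | Record review and survival contact (10.2); a note in 8.3 asks for efforts to document progression after treatment stops | Record review and survival contact in 10.2 are worded as *may*; no censoring rule or analysis set in 17.5.3 |

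**4. Effect on the Kaplan-Meier estimates.** A patient whose follow-up closes before infusion contributes nothing to a survival estimate counted from infusion. A patient whose follow-up closes at toxicity or deterioration after infusion is censored for a reason related to prognosis, and Kaplan-Meier assumes that does not happen.

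**5. Size, on assumptions.** Let k of 20 patients have an unknown 90-day outcome. The possible range of a proportion then widens by k/20, or 5 points per patient: 5, 10, 15 and 25 points for k = 1, 2, 3 and 5.

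Example: 4 events in 18 followed patients, 2 lost. Observed 4/18 = 22.2% (exact 95% CI 6.4% to 47.6%). Over all 20, the value lies between 4/20 = 20% and (4 + 2)/20 = 30%.

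If each patient stops with probability q, the chance of at least one stopper in 20 is 1 − (1 − q)^20:

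- q = 5%: 64% (1 patient expected)
- q = 10%: 88% (2 expected)
- q = 20%: 99% (4 expected)

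The documents give neither k nor q. Nor does every stopper go on to infusion or lose follow-up.

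**The case against.** The strongest reply is that 10.1 is about therapy and 10.2 is the follow-up section. Section 10.2 provides for 90 days after infusion and for survival data after protocol treatment ends. The safety rules in 18.3 and 18.4 are specific and mandatory, and a general list should not override them. The sentence on patients removed from the study does not describe a patient who stopped duvelisib and stayed on the pathway. The bullet on stopping study drug can be read as a duty to follow that event, not as a cap on other follow-up.

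Much of this stands. A reader might infer that CRS, neurotoxicity and ICU data will be missing for every patient with duvelisib toxicity. The documents do not support that: it would need 10.1 to override 18.3 and 18.4, and routine charts would still exist. Nor does 5.3 send these patients on to CAR-T; it says they *may* proceed.

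A reader might also infer that the losses would make safety and survival look better. Nothing in the documents links duvelisib intolerance to later CRS or ICU transfer, and early stoppers had less exposure. Stopping may also be uncommon: 4.2.4 puts median onset of AST/ALT elevation at 1.2 months and of diarrhea at 2.2 to 4 months, both beyond a 15-day course. Nor need the denominator fall below 20, because 17.5.1 replaces patients below its dose threshold, although replacement does not recover lost outcomes.

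The reply does not remove the conflict itself. Section 10.1 says when following stops, two rules in 10.2 can be read the same way, and the survival provision is only permissive.

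**Conclusion.** The point holds as an internal inconsistency with a limited consequence. Sections 10.1 and 10.2 contain rules that, read literally, end follow-up at toxicity, deterioration or a decision to stop treatment. They conflict with the 90-day follow-up in 10.2 and the recording rules in 18.3 and 18.4. The main exposure is 90-day PFS and OS; ICU transfer and tocilizumab or corticosteroid use are exposed to a lesser extent. Most CRS and toxicity data are protected.

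Any loss would be related to toxicity or deterioration, and so informative. Its size and direction cannot be derived from the documents; the 5 points per patient is arithmetic on an assumed number lost out of 20. The primary endpoint is not affected by this point, and no figure in the plan changes. The correction is still worth making, because it is cheap and protects the safety and survival summaries.

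**What to change.** Reconcile the passages by separating the end of duvelisib from the end of study follow-up in 10.1 and 10.2:

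- State that stopping duvelisib, toxicity or symptomatic deterioration does not end data collection.
- Follow every duvelisib-exposed patient who is infused, through the planned chart review, for adverse events, CRS and neurotoxicity, ICU transfer, progression and vital status to Day 90 after infusion.
- Follow exposed patients who are never infused for vital status to a stated equivalent date.
- Let follow-up end earlier only for death, withdrawal of consent or loss to follow-up.
- Make the survival collection in 10.2 mandatory to Day 90, and word the adverse event bullets there as additional to that follow-up.
- In 17.5.3, report items 6 to 8 on this set and state the censoring rule for PFS and OS.

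This concerns data collection only and changes no treatment rule. The cost is protocol wording plus chart review of a few more patients.

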10.2 Duration of follow-up

Patients will be followed for approximately 90 days after infusion of tisagenlecleucel product. Patient records may be reviewed until death to assess progression and survival. Survival information may be collected by clinic visit, email, or telephone after ending protocol treatment and until the study is terminated, the patient dies, or the patient is lost to follow-up.

A patient will be considered lost to follow-up if he/she fails to return for three scheduled visits and is unable to be contacted by the study site staff after three attempts at contact by phone.

The following actions must be taken if a patient fails to return to the clinic for a required study visit:
The site will attempt to contact the patient and reschedule the missed visit and counsel the participant on the importance of maintaining the assigned visit schedule and ascertain if the patient wishes to and/or should continue in the study.

Patients removed from study for unacceptable adverse event(s) will be followed until resolution or stabilization of the adverse event.

- Immunogenicity samples will be taken as per schedule of events

Protocol Title: Duvelisib Exposure to Enhance Immune Profiles of T Cells in Patients with Diffuse Large B Cell Lymphoma (DEEP T CELLS)

Patients who have not initiated a new antineoplastic regimen will have the following assessments:

- Radiologic tumor assessments at 90 days
- In case of a clinically significant AE, patient will be followed for safety until resolution or permanent sequelae of all toxicities attributable to study drug(s). If the patient discontinues study drug for a clinically significant AE, the patient will be followed until resolution of the AE or the event is considered to be stable and/or chronic.

11. Inclusion and Exclusion Criteria

11.1 Inclusion Criteria

- Patients must have a biopsy proven diagnosis of relapsed/refractory DLBCL or relapsed/refractory follicular lymphoma and be eligible to receive commercial tisagenlecleucel (Kymriah).
- 18 years of age or older
- ECOG <2
- Patients must have normal organ function as defined as:
 - Serum Cr <2.0 mg/dL
 - AST/ALT < 2x ULN
 - Total Bilirubin <2.0 mg/dL
- Patients with a hemoglobin >8 g/dL, platelet count >50K/mcl, an absolute neutrophil count (ANC) >1,000/mm³ and an absolute lymphocyte count (ALC) >300/mm³
- Completion of all previous therapy (including surgery, radiotherapy, chemotherapy, immunotherapy, or investigational therapy) for the treatment of their DLBCL or relapsed/refractory follicular lymphoma ≥ 2 weeks before the start of duvelisib. There is no limit on how many previous lines of treatment a patient may have received.
- The effects of duvelisib on the developing human fetus are unknown. For this reason, women of child-bearing potential (WOCBP) must have a negative serum or urine pregnancy test prior to starting therapy. WOCBP and men must agree to use highly effective contraception (hormonal or barrier method of birth control or abstinence) from enrollment into this study until at least 12 months after tisagenlecleucel infusion and until CAR-T cells are no longer present by qPCR on two consecutive tests (qPCR tests will be available upon request).
 - A woman of childbearing potential (WOCBP) is a sexually mature woman who: 1) has not undergone a hysterectomy or bilateral oophorectomy; or 2) has not been naturally postmenopausal for at least 24 consecutive months (i.e., has had menses at any time in the preceding 24 consecutive months).
 - WOCBP must have a negative pregnancy test within 24 hours of leukapheresis, lymphodepletion (if performed) and tisagenlecleucel infusion (if lymphodepletion not performed).
 - Should a woman become pregnant or suspect she is pregnant while she or her partner is participating in this study, she should inform her treating physician immediately.
 - All men treated or enrolled on this protocol must agree to use highly effective contraception from enrollment into this study until at least 12 months after tisagenlecleucel infusion and until CAR-T cells are no longer present by qPCR on two consecutive tests (qPCR tests will be available upon request).

The patient must be willing to comply with the fertility requirements and contraceptive options below:

- Female patients identified as WOCBP must be willing to use two adequate barrier methods of contraception to prevent pregnancy or agree to abstain from heterosexual activity (total abstinence).

Protocol Title: Duvelisib Exposure to Enhance Immune Profiles of T Cells in Patients with Diffuse Large B Cell Lymphoma (DEEP T CELLS)

- Total abstinence is permitted when this is in line with the usual practice and lifestyle of the patient. Periodic abstinence (i.e. calendar, ovulation, post-ovulation methods) and withdrawals are not acceptable forms of contraception.
- Sterilization:
 - Female sterilization includes having had surgical bilateral oophorectomy and/or bilateral salpingectomy with or without a hysterectomy, a total hysterectomy, or bilateral tubal ligation at least six weeks before taking study treatment. In case of oophorectomy alone, patients are eligible only when the reproductive status of the woman has been confirmed by a follow-up hormone assessment.
 - Male sterilization with vasectomy must occur at least 6 months prior to screening. For female patients on the study, the vasectomized male partner should be the sole partner.
- Use of oral (estrogen and progesterone), injected or implanted hormonal methods of contraception, or placement of an intrauterine device (IUD) or intrauterine system (IUS) or other forms of contraception that comparable efficacy (failure rate <1%). In case of oral contraception, the woman should be stable on the same pill for a minimum of 3 months prior to enrollment on the study.
- Sexually active males must use a condom during intercourse from enrollment into this study until at least 12 months after tisagenlecleucel infusion and until CAR-T cells are no longer present by qPCR on two consecutive tests (qPCR tests will be available upon request). A condom is required of all sexually active male patients to prevent them from fathering a child AND to prevent delivery of study treatment via seminal fluid to their partner.

The patient must be willing to comply with the following requirements:

- Patients must agree not to donate blood, sperm/ova or any other organs while taking protocol therapy and for at least 12 months after stopping treatment.
- Willingness and ability of the patient to comply with scheduled visits, drug administration plan, protocol specified laboratory tests, other study procedures and study restrictions.
- Evidence of personally signed informed consent indicating that the subject is aware of the neoplastic nature of the disease and has been informed on the procedures to be followed, the experimental nature of the therapy, alternative, potential risks and discomforts, potential benefits and other pertinent aspects of study participation.

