T cells can be categorized based upon whether their T cell receptor (TCR) recognizes antigen by major histocompatibility complex (MHC) in an independent or dependent manner. Alpha Beta T cells contain a TCR that recognize peptide presented by class I or II MHC, whereas Gamma Delta T cells recognize antigens independent of MHC. Gamma Delta T cells are a small and unique population of T cells that comprise less than 5% of the total T cell population.²¹ They generally do not express CD4 or CD8 and have the unique role of serving as both effector T cells and initiating and maintaining adaptive immune responses.²² Gamma-Delta T cells are able to secrete cytokines, including IL-4 and TNFa, that can directly attack and kill tumor cells. They can also act as antigen presenting cells (APCs) and have the capacity to induce CD4+ and CD8+ antigen specific T cells.²³ Pre-clinical studies have shown that gamma delta CAR-T cells have a more naïve T cell phenotype and that their cytotoxicity was equivalent to alpha beta CAR-T cells.²⁴

Alpha Beta(+) TCR T cells are the predominant T cells comprising >95% of T cells and can be further sub-categorized into helper, cytotoxic, memory or regulatory T cells.²³ Naïve T cells are antigen inexperienced and are characterized by the expression of CD45RA, CD62L and the co-stimulatory molecules CD27 and CD28. Central memory T cells, which have previously encountered an antigen, express CD45RO, CD27 and CD62L and thus, retain their proliferative capacity. Effector memory T cells lack CD27 and CD62L which reduces their proliferative capacity.²⁵

One unintended consequence of cytotoxic chemotherapy, is depletion of healthy T cells, including naïve and central memory T cell subsets, that have the most potent ability to respond to malignant antigens, have greater expansion potential and greater anti-cancer activity.²⁶⁻²⁷ Numerous studies have shown superior persistence and anti-tumor activity with minimally differentiated T cells, including naïve, stem cell and central memory T cells.²⁸⁻³⁰

These observations also apply to CAR T cells, as study of determinant of outcomes revealed that frequencies of memory and naïve cells prior to CAR T manufacture appear to be associated with remissions.³¹

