5.1 Study Design

This is an open-label pilot clinical trial prospective study of treating patients with relapsed/refractory DLBCL or relapsed/refractory follicular lymphoma with duvelisib at a dose of 25 mg p.o. b.i.d. for 8 to 15 days prior to collection of mononuclear cells by apheresis for the purpose of CAR-T manufacturing. The intended duration of duvelisib exposure is 2 weeks. The duration of duvelisib may be adjusted to a period between 8 and 15 days depending upon the schedule of apheresis, with the last dose of duvelisib on the day of apheresis.

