5.6 Study Procedures

Screening Phase:

All screening evaluations must be conducted and reviewed by the primary investigator to confirm that patients meet the eligibility criteria. The following procedures will be performed during the screening visit:

- Informed Consent
- Medical History, Physical Exam, Assessment of Performance Status
- Electrocardiogram (EKG)
- Labs: Complete Blood Count (includes hemoglobin, platelets, and white blood cell count with differential), Comprehensive metabolic panel (includes sodium, potassium, chloride, creatinine, AST, ALT total bilirubin and alkaline phosphatase), Coagulation Testing (PT/INR, PTT), Thyroid Stimulating Hormone (TSH)
- T cell count phenotyping via flow cytometry
- Pregnancy Test (for women of childbearing potential)
- Infectious Work Up: HIV antigen/antibody, Hepatitis C antibody and Hepatitis B antibodies with viral loads (if known history of treated Hepatitis B or C).
- COVID-19 screening by PCR: During the screening period within 7 days of initiation of duvelisib.
 - If asymptomatic and PCR negative: Ok to proceed
 - If PCR+ and:
 - Asymptomatic: Wait 14 days and initiate duvelisib
 - Symptomatic: Wait 14 days *after resolution of symptoms* and initiate duvelisib
 - A negative PCR is not required after a 14 day wait period

Please see section 1.2 (Table 1) for schedule for screening and pre-screening assessments. Pre-screening assessments will be completed within two weeks of initiation of duvelisib treatment.

Treatment Phase:

Procedures to be conducted during the treatment phase of the study are presented in the Schedule of Assessments (Section 1.3, Table 1).

- Brief medical history
- Symptom-directed physical exam

Protocol Title: Duvelisib Exposure to Enhance Immune Profiles of T Cells in Patients with Diffuse Large B Cell Lymphoma (DEEP T CELLS)

- ECOG Performance Status
- Vitals signs, weight
- Review of prior/concomitant medications
- Labs: Complete Blood Count (includes hemoglobin, platelets, and white blood cell count with differential), Comprehensive metabolic panel (includes sodium, potassium, chloride, creatinine, AST, ALT total bilirubin and alkaline phosphatase), Thyroid Stimulating Hormone (TSH)
- T cell count and phenotyping (days 1 and 15 only)
- AE monitoring (days 8 and 15)

Post CAR-T 19 Cell Infusion Assessments

Procedures to be conducted during the post CAR-T 10 cell infusion phase of the study are presented in the Schedule of Assessments (Section 1.3 Table 2).

- CAR T 19 PCR

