17.5.2 Analysis of Primary Endpoints

All patients that complete >75% of planned duvelisib doses and undergo leukapheresis within 2 weeks of duvelisib treatment completion will be included in the final analysis of the primary endpoint. The primary endpoint of the study to estimate the fold-change increase in CD27/CD28 double positive T cells following *in vivo* exposure to duvelisib from baseline to day 15. Our in vitro studies have shown that culturing DLBCL patients' T cells with 14 days of duvelisib increased the amount of CD27/CD28 double positive T cells from 12.2% to 32.7% (Petersen, et al, supplemental data). However, there are currently no *in vivo* background data to benchmark the expected fold-change CD27/CD28 double positive T cells over a 14-day window. Therefore, with 20 patients, this pilot study will be based on estimation on the fold change increase only and will not include a formal evaluation of the change against a null unpromising fold-change. However, we will consider this study promising if there is at least a two-fold increase in CD27+/CD28+ in at least 75% of patients.

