17.5.4 Demographics and Baseline Characteristics

Summary statistics and frequencies for the following characteristics will be collected:

- ECOG
- Race
- Age
- Sex
- Past Medical History
- Current Medication List
- Number type, dose and dates of prior treatments
- Prior autologous stem cell transplant (ASCT)
- Molecular Subgroup (Activated B cell vs Germinal Center)
- BCL-2 alterations/overexpression
- BCL-6 alterations/overexpression
- C-MYC alterations/overexpression
- Double/Triple Hit Status
- Disease Stage
- History of lymphoma bone marrow involvement

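### The uncontrolled fold change could mix a duvelisib effect with T-cell recovery or other drift, because 'baseline' is not tied to a pre-dose Day 1 sample and no analysis shows the drug-free change

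*Combined protocol and SAP*

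**What the plan says.** Section 5.1 describes a one-group design: "This is an open-label pilot clinical trial prospective study of treating patients". Patients take duvelisib for 8 to 15 days before apheresis, with the last dose on the day of apheresis. Section 17.5.2 defines the primary endpoint as the fold change in CD27/CD28 double-positive T cells "from baseline to day 15". It concedes that there are no in vivo data on how this quantity changes over 14 days, and states that "with 20 patients, this pilot study will be based on estimation on the fold change increase only". It still sets a benchmark: "we will consider this study promising" if at least 75% of patients show at least a two-fold rise.

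On prior therapy, Section 11.1 requires completion at least "2 weeks before the start of duvelisib". Section 3 (T cells and Cancer Immunotherapy) names "depletion of healthy T cells" as a consequence of chemotherapy, including the naive and central memory subsets. It describes naive cells as expressing CD27 and CD28, and central memory cells as expressing CD27. It adds that heavily pre-treated DLBCL patients have a higher proportion of double-negative T cells than newly diagnosed patients.

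The sections disagree on sampling. Section 5.6 lists phenotyping at screening and, in the treatment phase, "T cell count and phenotyping (days 1 and 15 only". Table 1 in Section 1.3 has one pre-drug column (Days -14 to 0), then Day 8 and Day 15, with no Day 1 column. Section 5.7 lists phenotyping at screening and before apheresis only. Section 17.5.4 collects "Number type, dose and dates of prior treatments", for summary only.

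**The concern.** With one arm and no benchmark, anything that moves the CD27/CD28 proportion between the two samples counts as response. Recovery from recent chemotherapy is a plausible candidate on the protocol's own background, since prior treatment is linked there to loss of the measured cells. A screening sample used as baseline adds up to two drug-free weeks to the interval.

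Nothing in Section 17.5 would reveal such drift. The secondary Wilcoxon signed-rank test uses the same baseline-to-Day 15 contrast, and treatment dates do not enter the primary analysis. At stake is how the two-fold/75% benchmark is read. A result on either side of it could partly reflect change that would have happened without duvelisib.

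**Working it through.** **The plan's own figures.** There is no power, alpha or precision target to reproduce. The benchmark is 0.75 × 20 = 15 of 20 patients. The in vitro change quoted in 17.5.2 is 32.7/12.2 = 2.68-fold.

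**Share of the interval on drug.** Inputs: earliest screening sample Day -14 (Table 1), exposure of 8 to 15 days with the last dose on the day of apheresis (5.1), phenotyping before apheresis (5.7). Each dosing day counts as one day on drug.
- 8 days of drug, sample on the last-dose day: 14 + 8 = 22 days; 8/22 = 36%.
- 15 days of drug, sample on the last-dose day: 14 + 15 = 29 days; 15/29 = 52%.
- Using the two-day allowance to apheresis in 7.1: 8/24 = 33% and 15/31 = 48%.

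These are extremes for the earliest permitted screening sample; a later one raises the share. With a pre-dose Day 1 baseline and sampling on the last-dose day, the whole interval is on drug.

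**Could drift matter to the benchmark?** This is an illustration on assumptions. Let log2 fold change be normal with mean log2(drug effect × drift) and SD s. Then p = P(log2 fold change ≥ 1), and the benchmark is met with probability P(X ≥ 15), where X ~ Binomial(20, p). The documents give neither s nor the drift. The main column uses s = 0.75, and the last gives results for s = 0.5 and s = 1.0.

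| Drug effect | Drift | p (s = 0.75) | P(benchmark met), s = 0.75 | s = 0.5; s = 1.0 |
|---|---|---|---|---|
| none | 1.5 | 0.29 | about 0% | about 0%; about 0% |
| none | 2.0 | 0.50 | 2.1% | 2.1%; 2.1% |
| 2.0 | none | 0.50 | 2.1% | 2.1%; 2.1% |
| 2.0 | 1.25 | 0.67 | 29.5% | 57.7%; 18.2% |
| 2.0 | 1.5 | 0.78 | 74.3% | 97.3%; 49.8% |
| 2.68 | none | 0.71 | 47% | 81%; 29% |
| 2.68 | 1/1.25 = 0.8 | 0.55 | 5.9% | 9.2%; 4.6% |

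The benchmark concerns individual patients. A median change of exactly two-fold gives p = 0.5, and P(X ≥ 15) = 21,700/1,048,576 = 2.1%. Drift alone would have to exceed two-fold to meet the benchmark with any regularity. Moderate drift on top of a real effect can move the result a long way, upward or downward.

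**Why the drug-free change should be shown and not subtracted.** Let T be days on drug and L the days from screening to Day 1, with equal independent sample variance σ² on the log scale and linear drift. The corrected contrast has variance σ²[1 + (1 + T/L)² + (T/L)²], against 2σ² for the plain on-drug change. For T = 14 the standard error grows by:
- L = 14: √(6/2) = 1.73
- L = 7: √(14/2) = 2.65
- L = 3: √(54.9/2) = 5.24

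The gap is not fixed and can be anything from about 1 to 14 days, so subtraction would often add more noise than it removes bias.

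**The case against.** The strongest reply is that the plan already presents itself as estimation only, admits the missing in vivo benchmark and makes no formal test. Two weeks is a minimum washout, and recent chemotherapy is not required. Section 11.2 also excludes chemotherapy within 2 weeks of study entry (6 weeks for nitrosoureas or mitomycin C) and unrecovered toxicity above Grade 1, and Section 11.1 sets neutrophil and lymphocyte floors. The Section 1.2 schema labels Day 1 as baseline assessments. All of this stands and makes the concern a possibility only. It does not remove it: the schema defers to Section 1.3, which has no Day 1 column, and 17.5.2 still applies its benchmark to the raw change.

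Three stronger readings are tempting, but the documents do not support them.
- A reader might infer that the bias must favour a promising result. The endpoint is a proportion of T cells, so a recovering count need not raise it. Section 3 says chemotherapy depletes these subsets, not that their share rebounds within weeks.
- A reader might infer that a 1.25-fold or 1.5-fold drift, with a drug effect making up the rest of two-fold, is enough to meet the benchmark. That treats an average of two-fold as sufficient; the working shows it would succeed about 2% of the time.
- A reader might combine 8 days of drug with a Day 17 sample from Table 1's window and get 8/31 = 26% on drug. That conflicts with the apheresis timing in 5.1 and 7.1 and with pre-apheresis sampling in 5.7.

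It is also fair that the Day 1 sample is not secure. Only 5.6 lists it, and the sampling schema in Appendix D is a figure not available to this review.

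**Conclusion.** The point holds as a limit on interpretation: the fold change in 17.5.2 could mix a duvelisib effect with recovery or other drift, and the plan neither fixes the baseline nor shows the drug-free change. With the earliest permitted screening sample as baseline, about 36% to 52% of the interval is on drug. This assumes sampling on the last-dose day, and the figures fall to 33% and 48% with the two-day apheresis allowance. The size and direction of any drift are unknown; the probabilities above rest on assumed drifts and SDs and show only that moderate drift could matter. No calculation in the plan is wrong. The change is worth making because it is cheap. It cannot make the trial controlled: drift that continues during dosing stays in the estimate even with a Day 1 baseline.

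**What to change.** 1. Reconcile Section 5.6 with Table 1 and Section 5.7 by keeping the pre-dose Day 1 phenotyping sample in all three.
2. In 17.5.2, define that sample as baseline for the primary fold change and for the two-fold/75% benchmark.
3. Report each patient's screening-to-Day 1 change, with its length in days, beside the on-drug change and without subtracting it.
4. Show fold change against days since last therapy, from the dates collected under 17.5.4.
5. State that a promising result cannot be attributed to duvelisib alone if the drug-free change or the time-since-therapy pattern is material.

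The cost is at most one extra phenotyping draw per patient, at a visit where 5.7 already lists Day 1 blood tests, plus a short descriptive analysis. Sample size, eligibility and treatment are unchanged. The main weakness is that the drug-free interval of about 1 to 14 days is a limited control when short, which is why its length should be reported with it.
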